3.4.2 Tools Used for Data Collection

Data will be recorded in a Subject Diary Card by appropriately trained study staff and entered on Case Report Forms (CRFs).

The subject Diary Card will be the only source document allowed for solicited local and systemic adverse events (including body temperature measurements), starting after the initial 60 minute post-vaccination period at the clinic. The following additional rules apply to documentation of safety information collected in the Diary Card.

The Investigator or delegated staff should monitor the Diary Card status throughout the study for compliance and any solicited local and systemic adverse events that were of concern to the subject.

1. No corrections or additions to the information recorded by the trained study staff within the Diary Card will be allowed after it is delivered to the site.
2. Any blank or illegible fields on the Diary Card must be described as missing in the CRF.

Case Report Forms

This study utilizes Case Report Forms (CRFs) to collect study-related data from each subject. A qualified site staff member(s) is required to enter subject data in the CRFs in English based on the medical information available in each subject's source record.

Data should be entered into the CRF in a timely fashion following each subject's clinic visit, study procedure, or home visit. Each subject's CRF casebook will be compared with the subject's source records by a GVGH-approved study monitor (or designee) over the duration of the study in order to ensure data collection accuracy.

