8. STATISTICAL CONSIDERATIONS

8.1 Endpoints

8.1.1 Primary Endpoint(s)

8.1.1.1 Primary Safety Endpoint(s)

The safety profile of the two vaccine doses and control(s) will be assessed through measurement of the following:

- a. Number and percentage of subjects with solicited local and systemic adverse reactions during 7 days following each vaccination.
- b. Numbers and percentage of subjects with deviations from normal ranges of safety laboratory data after each vaccination.
- c. Number and percentage of subjects with reported unsolicited adverse events during 28 days following each vaccination.
- d. Number and percentage of subjects with reported SAEs throughout the study duration.
- e. Number and percentage of subjects with reported reactive arthritis or neutropenia (AESIs).

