- Physical examination must be performed by a qualified health professional in accordance with local regulations and licensing requirements designated within the Site Responsibility Delegation Log.
- Compliance with Exclusion/Inclusion criteria should be verified.
- In case of neutropenia, Complete Blood Count to be repeated on a weekly basis until resolution. If neutropenia occurs at the last study visit, Complete Blood Count to be repeated on a regular basis until resolution.

- e. A post-injection local and system adverse event and body temperature measurement will be performed approximately 30 and 60 minutes after each vaccination during the clinic visit.
- f. Beginning in the evening following study vaccine administration (approximately 6 hours), and daily thereafter through the following 6 days, solicited local and systemic adverse events including body temperature measurements and use of analgesics/antipyretics will be reported by field workers in a diary card based on subject's observation and interview.
- g. All unsolicited adverse events will be captured through 28 days following each vaccination
- h. SAEs, AESI and AEs leading to study or vaccine withdrawal will be collected through entire study duration.

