7.7 Overview of Analysis Sets by PD Code

Table 7.7-1: Safety Sets

PD code	PD Description	Study Objective/ Period	All Exposed Set	Overall Safety Set	Safety Set, Unsolicited AEs, All study period	Safety Set, Solicited AEs, Period 1, T30-D7	Safety Set, Solicited AEs, Period 2, T30-D7
			Exclusion code	EXPFL	SAFFL	SSU10FL	SSS10FL
100	Study vaccine not administered AT ALL	All Study	EXC	EXC	EXC	EXC	EXC
115	Subject did not provide any post-vaccination unsolicited safety data – All study period	All Study			EXC		
116	Subject did not provide any post-vaccination solicited safety data	All Study				EXC	EXC
116.1	Subject did not provide any post-vaccination solicited safety data after 1st vaccination	Period 1				EXC	
116.2	Subject did not provide any post-vaccination solicited safety data after 2nd vaccination	Period 2					EXC

EXC = excluded from this analysis set.

Table 7.7-2: Immunogenicity Sets

PD code	PD Description	Study Objective/ Period	All Exposed	FAS 1 - day 28 after 1 st vac	FAS 2 - day 28 after 2 nd vac	PPS X -	PPS 1 - day 28 after 1 st vac	PPS 2 - day 28 after 2 nd vac	
				Exclusion code	EXPFL	FAS10FL	FAS20FL	PPSX0FL	PPS10FL
100	Study vaccine not administered AT ALL	All Study	EXC	EXC	EXC	EXC	EXC	EXC	EXC
110	Serological results are not available	All Study		EXC	EXC	EXC	EXC	EXC	EXC
110.3	Serological results are not available for visit 3 (post 1 st vac)	Visit 3		EXC		EXC	EXC		
110.5	Serological results are not available for visit 5 (post 2 nd vac)	Visit 5			EXC			EXC	
112	Obvious deviation from Laboratory Manual or error in laboratory data								
112.3	Incoherence between CRF and CLS database in terms of sample availability at visit 3	Visit 3				EXC	EXC		

PD code	PD Description	Study Objective / Period	All Exposed	FAS 1 - day 28 after 1 st vac	FAS 2 - day 28 after 2 nd vac	PPS X -	PPS 1 - day 28 after 1 st vac	PPS 2 - day 28 after 2 nd vac
				EXPF	FAS10FL			
112.5	Incoherence between CRF and CLS database in terms of sample availability at visit 5	Visit 5						EXC
120	Randomization failure		EXC	EXC	EXC	EXC	EXC	EXC
120.2	Subject received another vaccine than allocated (Actual Arm different from Planned Arm) at 1 st vacc	All study		EXC	EXC	EXC	EXC	EXC
130	Randomization code was broken	All study				EXC	EXC	EXC
140	Vaccination not according to protocol					EXC	EXC	EXC
140.1	Administration of temperature-deviated vaccine					EXC	EXC	EXC

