8.2.1 Safety Data

Solicited adverse events: The solicited study period will be '30 min - day7'.

No imputation methods will be used to address missing values.

Unsolicited adverse events: The unsolicited adverse events will be analyzed in the entire study period.

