13.2 Solicited Local and Systemic Adverse Events

For details please refer to [section 6.5 of the protocol](#).

All solicited local and systemic adverse events will be analyzed. Implausible measurements will not be taken into consideration in the analysis but listed in the Appendix (see [section 6.3](#)).

Solicited adverse events will be reported at 30 minutes, 2 hours, 6 hours on day 1 and then daily until day 7 using structured diaries. The analyses of solicited adverse events will be done separately for the period 30 minutes – day 7. In addition solicited adverse events ongoing after day 7 will be presented as unsolicited AE.

For erythema and induration, recorded originally as diameters (mm), the following categorization will be used to summarize the data:

Type II: Grade 0 (< 25 mm), any (25-50 mm, 51-100 mm, >100 mm)

Body temperature will be broken down by route of measurement according to the recommendations of the Brighton collaboration and will be summarized according to the 3 schemes described below:

- by 0.5 °C increments: <36.0, 36.0 - 36.4, 36.5 - 36.9, 37.0 - 37.4, 37.5 - 37.9, 38.0 - 38.4, 38.5 - 38.9, 39.0 - 39.4, 39.5 - 39.9, ≥40.0°C
- by 1.0 °C increments: <36.0, ≥36.0-<37.0, ≥37.0-<38.0, ≥38.0-<39.0, ≥39.0-<40, ≥40°C
- <38.0, ≥38.0 °C

Fever, defined as a body temperature of ≥38°C irrespective of route of measurement, will be integrated to the summaries as a systemic adverse event.

The analyses will encompass summaries of the data on five levels:

1. Daily reports of subjects with solicited adverse events.
2. Time of first onset of solicited adverse events.
3. Solicited adverse events, maximum event severity by event and interval (30 min – day 7).
4. Duration of solicited adverse events, including ongoing AE after Day 7.
5. Solicited adverse events and indicators of solicited adverse events, occurrence of at least one event by category (local, systemic) and interval (30 min- Day 7).

For each of the time points or time intervals presented in the summaries, only subjects with at least one plausible observation (i.e., any non-missing values but excluding “Not done/unknown” and implausible values) for the solicited adverse events in the interval of interest will be considered. Subjects without plausible data (i.e. missing values or

reported as “Not done/unknown” and implausible values) will be removed from the denominator to prevent a downward bias (towards zero).

Level 1: Daily reports of solicited adverse event

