For each of the time points only subjects with at least one plausible observation (i.e., any non-missing values but excluding “Not done/unknown” and implausible values) for the solicited adverse event in the interval of interest will be considered. Subjects without plausible data (i.e. missing values or reported as “Not done/unknown” and implausible values) will be removed from the denominator in order to prevent a downward bias (towards zero). Data collected will be summarized (frequencies and percentages of subjects) by vaccine group, solicited adverse event, vaccination number and time point.

Level 2: Time of first onset of solicited adverse events

The **time of first onset** is defined, for each subject, for each solicited adverse event, as the time point at which the respective solicited adverse event first occurred. For erythema and induration the following threshold(s) will be used ≥ 25 mm. The summary will provide the frequencies and percentages of subjects with first onset of each solicited adverse events by vaccine group and by each time point.

For each vaccination the first onset of the adverse event will be used for each subject. For any vaccination the worst adverse event across all vaccinations per time point will be used. Note, ‘not done’ is treated identical to ‘missing’.

Level 3: Solicited adverse events, maximum event severity by event and interval

The **maximum event severity** will be defined if there is at least one plausible non-missing observation (excluding “Not done/unknown” and implausible values) within this time interval. Each subject’s data will be aggregated across the time points of the interval and summarized according to the maximal severity observed for each adverse event, followed by a summary across subjects for each vaccine. Subjects without any solicited adverse events in the interval, i.e., missing values at each of the requested time points, will be removed from the denominator.

Level 4: Solicited adverse events, occurrence of at least one event by category (local, systemic) and interval.

The **occurrence of at least one solicited adverse event** is defined as “any” for a subject if he/she reports greater than “none” (≥ 25 mm for erythema and induration) for the respective event and “none” otherwise. The occurrence of at least one solicited adverse event (i.e., none versus any) will be summarized by category (i.e., local, systemic, any),

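### The one-reading rule for solicited events (SAP 13.2) can count a subject with clinic readings but no diary data as reaction-free for seven days

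*SAP*

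**What the plan says.** Endpoint (a) in Protocol 8.1.1.1 is "Number and percentage of subjects with solicited local and systemic adverse reactions during 7 days following each vaccination".

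SAP 8.2.1 fixes the window: "The solicited study period will be '30 min - day7". The set label in SAP Table 7.7-1 matches it: "Safety Set, Solicited AEs, Period 1, T30-D7". SAP 8.2.1 adds: "No imputation methods will be used to address missing values".

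SAP 13.2 sets the denominators. Subjects without plausible data in the interval of interest "will be removed from the denominator to prevent a downward bias (towards zero"). Under Level 3, maximum severity is defined "if there is at least one plausible non-missing observation", and a subject leaves the denominator only if values are missing at every time point. Under Level 4 (the fifth item in that section's opening list), a subject with no reported event is 'none'.

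Note e to the Times and Events Table (SAP section 3) says that a local and systemic event check and "body temperature measurement will be performed approximately 30 and 60 minutes after each vaccination during the clinic visit". Protocol 5.2.1 sends what is found in that hour to the source document. Protocol 3.4.2 makes the Diary Card the sole source only after those 60 minutes, and adds: "Any blank or illegible fields on the Diary Card must be described as missing in the CRF".

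**The concern.** The denominator rule is meant to stop unobserved subjects from diluting the reaction rate. It works only for a subject with nothing recorded in the interval. Because the interval opens at 30 minutes, a clinic reading taken before the subject goes home satisfies the rule by itself. If that reading is event-free and no diary data follow, the subject is reported as having no reaction through day 7, although almost none of that period was observed. Nothing is formally imputed, but the result is the same as scoring the unobserved days event-free.

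The tables affected are those that deliver a primary safety endpoint, and the error runs towards understating reactogenicity. If diaries were missing more often in one arm, the comparison with control would also shift.

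**Working it through.** **The plan's own figures.** The protocol synopsis gives 20 evaluable subjects per group, a 10% event rate and an 87% chance of seeing at least one event. 1 − 0.9^20 = 0.878, so the figure reproduces, apparently cut down from 87.8%. 20/(1 − 0.15) = 23.5, rounded up to 24 per group. Neither figure depends on the denominator rule. They supply the arm size used below.

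**Path of a clinic-only subject**
1. The 30- and 60-minute readings exist and, on the protocol text, sit outside the diary.
2. Blank diary fields are entered as missing.
3. Level 3 finds one plausible value, so severity is defined, as absent. Level 4 finds no reported event and codes 'none'.
4. The Solicited Safety Set (SAP 7.5) admits any solicited data. Deviation codes 116, 116.1 and 116.2 exclude only subjects with none, so the subject stays in.
5. Level 1 drops the subject at each time point where the value is missing, so the daily tables are unaffected.

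**Size.** Let m be the share of subjects with clinic-only data, p the true 7-day rate and q the event rate at the clinic reading.

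- Reported rate = (1 − m)p + mq
- Bias = −m(p − q)

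A reaction in the clinic is also a 7-day reaction, so q cannot exceed p and the bias is never positive. With k clinic-only subjects in an arm of 24 and q = 0, the reported rate is p(24 − k)/24, a relative bias of −k/24.

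| k of 24 | Relative bias | True 30% reported as | True 50% reported as |
|---|---|---|---|
| 0 | 0 | 30.0% | 50.0% |
| 1 | −4.2% | 28.8% | 47.9% |
| 2 | −8.3% | 27.5% | 45.8% |

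With q = 5%, p = 50% and k = 1, the bias is −(1/24)(0.45) = −1.9 points, giving 48.1%.

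The documents give neither m nor q. Over an assumed range of m = 5%, 10% and 15%, with p = 50% and q = 0, the reported rates are 47.5%, 45.0% and 42.5%. With q = 5% and m = 15% the rate is 43.25%.

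**Missingness.** The formula takes diary loss as unrelated to outcome. If it is related, p and q become the clinic-only subjects' own rates. The bias against the whole-arm truth is then −m times their difference, which still cannot be positive.

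**The case against.** The strongest reply is that the situation may hardly arise. Trained field workers fill in the card at daily home visits from about 6 hours to day 7 (Protocol 5.3.1), CRF entry is to follow promptly (3.4.2), and the card is reviewed at the day-7 clinic visit (5.3.2). This stands: m is probably small, and if no diary is missing the bias is zero.

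Second, SAP 13.2 itself says that solicited events are reported at 30 minutes, 2 hours and 6 hours and then daily in structured diaries. On that reading a lost diary takes the 30-minute value with it, and the subject leaves the denominator. Protocol 3.4.2 and 5.2.1 and note e point the other way. The documents conflict, so the point is conditional on the protocol's reading.

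Third, a reader might infer that missing diaries would go unseen, because SAP 13.1.1 drops the diary completeness analysis. The documents do not support that. Level 1 denominators would fall at every post-clinic time point. What remains true is that the interval tables carrying endpoint (a) would not show it.

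Fourth, the trial is descriptive, with no hypotheses and no success criterion, and one clinic-only subject moves a true 50% by about 2 points, while the exact 95% interval for 12/24 runs from 29% to 71%. This limits the consequence. It does not justify a rule that misses its own stated purpose when the remedy needs no new data.

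**Conclusion.** The concern holds in conditional form. If the early readings are clinic source data, the one-reading rule keeps clinic-only subjects in the Level 3 and Level 4 denominators, and those without a clinic reaction count as 'none'. The bias is −m(p − q): never upward, zero with no missing diaries, and about −4% of the rate per clinic-only subject in an arm of 24 when q = 0. A reaction seen in the clinic is still counted.

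A reader might take the 24-to-20 drop-out allowance as four clinic-only subjects per arm. A true 50% would then be reported as 0.5 × 20/24 = 41.7%, and with all four in one vaccine arm against 30% in control, a 20-point difference would appear as 11.7 points. The documents do not support this as a forecast. The allowance covers the whole trial of about two months. Subjects who leave after day 7 can have a full first-dose diary, and those who leave before the second dose have no second clinic reading. Complete diary loss by drop-out requires loss between leaving the clinic and the first home visit, about 6 hours after injection. Nothing suggests that such losses would concentrate in one arm of an observer-blind trial.

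The interval gap matters too. Protocol 8.4.2.1.2 requires day 1–3, day 4–7 and day 1–7 summaries. A day 4–7 table would drop a clinic-only subject, but SAP 13.2 carries only the single interval.

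**What to change.** Amend SAP 8.2.1 and 13.2 (Levels 3 and 4), together with the first- and second-dose solicited set definitions in SAP 7.5.

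1. Keep the 7-day percentage over 30 minutes to day 7, so that clinic reactions still count. Require at least one plausible Diary Card reading for that event between 6 hours and day 7 to enter the denominator. List separately any clinic-only subject who reacted in the clinic. Do not move the endpoint to 6 hours–day 7: that would drop reactions seen only in the clinic and depart from endpoint (a).
2. Footnote, by arm and dose, the number of clinic-only subjects and the diary days observed. The second count is needed because one reading does not cure a partly blank diary, whose unobserved days are still treated as event-free.
3. Restore the protocol's day 1–3 and day 4–7 summaries, each with its own denominator. Day 1–3 needs the same post-clinic condition, because the clinic reading falls inside it.
4. Reconcile SAP 13.2 with the protocol and note e on when the early readings are taken and where they are recorded. The denominator depends on it.

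The cost is SAP wording, one denominator flag and two added summaries, with no new data. The 7-day denominator may be slightly smaller than the exposed set. The revised rate is unbiased for p only if diary loss is unrelated to outcome, so the footnoted counts should stay even if they are zero.

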13.3 Unsolicited Adverse Events

All AEs occurring during the first 28 days after each vaccination, including the day of vaccination, and all AEs leading to withdrawal, all SAEs and all AEs of special interest occurring at any time during the study will be recorded according to the protocol-specified reporting rules.

The original verbatim terms used by investigators to identify adverse events in the CRFs will be mapped to preferred terms using the MedDRA dictionary. The unsolicited adverse events will then be grouped by MedDRA preferred terms into frequency tables according to system organ class. Adverse events judged by the investigator as at least possibly related to study vaccine will be summarized by vaccine group, according to system organ class and preferred term within system organ class. When an unsolicited adverse event occurs more than once for a subject, the maximal severity and strongest relationship to the vaccine group will be counted.

Only vaccine-emergent adverse events (see [section 8.7](#) for definition) will be analyzed, i.e., excluding those after a subject has given informed consent but before vaccination. The selection of unsolicited adverse events and the assignment to time intervals will be done by day of onset and not by days ongoing/persisting.

The summaries will be presented by period of onset and will include frequency distributions of the different adverse events:

- Onset between day 1 and study termination.

The analysis of unsolicited adverse events comprises the following categories:

- Any unsolicited adverse event.
- Possibly or probably related unsolicited adverse events.
- Unsolicited adverse events leading to death.
- Serious adverse events.
- Possibly or probably related serious adverse event.
- Unsolicited adverse events leading to premature withdrawal from study.

- Unsolicited adverse events leading to dose reduction, interruption or delay in study vaccination.
- Unsolicited adverse events leading to hospitalization.

Solicited adverse events continuing beyond day 7 will be coded by MedDRA and combined with the respective unsolicited adverse events.

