8.4.2.1.3 Analysis of Unsolicited Adverse Events

This analysis applies to all adverse events occurring during the study, judged either as probably related, possibly related, or not related to vaccination by the investigator, recorded in AE CRF, with a start date on or after the date of first vaccination. AE starting prior to the first vaccination will only be listed. The original verbatim terms used by

investigators to identify adverse events in the CRFs will be mapped to preferred terms using the MedDRA dictionary. The adverse events will then be grouped by MedDRA preferred terms into frequency tables according to system organ class (SOC).

All reported adverse events, as well as adverse events judged by the investigator as at least possibly related to study vaccine, will be summarized according to SOC and preferred term within SOC. These summaries will be presented by vaccination group. When an adverse event occurs more than once for a subject, the maximal severity and strongest relationship to the vaccine group will be counted.

Separate summaries will be produced for the following categories:

- Serious adverse events and adverse events of special interest.
- Adverse events that are possibly or probably related to vaccine.
- Adverse event leading to withdrawal.

Data listings of all adverse events will be provided by subject. In addition, adverse events in the categories above will be provided as listed data.

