7.5 Safety Set

Solicited Safety Set

All subjects in the Exposed Set with any solicited adverse event data and/or indicators of solicited adverse events (e.g., use of analgesics/antipyretics)].

For the by vaccination tabulations, solicited safety sets will be defined as follows:

- Solicited safety set #1 for post-injection reactions after the first dose (SOL 1)
- Solicited safety set #2 for post-injection reactions after the second dose (SOL 2)

Unsolicited Safety Set

All subjects in the Exposed Set with unsolicited adverse event data.

In this respect, a confirmation of no AE is considered as adverse event data; hence subject is to be included.

Overall Safety Set

All subjects who are in the solicited safety set and/or in the unsolicited safety set.

In case of vaccination error, subjects will be analyzed as “treated” (i.e., according to the vaccine a subject receives, rather than the vaccine to which the subject is randomized).

If a subject received the correct study vaccine (dose, batch) but from another ongoing study at the site then the subject’s safety data should be included in the safety analysis.

If a subject is unblinded during the study, he/she will be included in all the safety sets.

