- **Emergence during vaccination phase:** start date on or after the first date of injection of study vaccine or, adverse event increase in severity including to “serious” adverse event.

If start date is equal to the first date of injection then “timing” variable (“On injection day, before injection”/“On injection day, after injection”) will be used to define whether the adverse event occur before or after the injection.

If there are several vaccinations, the adverse event will be associated with the most recent vaccination.

If an adverse event start date is missing or unknown, the adverse event will be considered as emergent.

When start and/or end dates of an adverse event are only partially known, adverse events will be categorized as emergent before, during, or after vaccination phase using the following rules:

- If the partial end date is before ($<$) the first study vaccination (i.e., year or year & month is/are before the first study vaccination year or year & month) then the adverse event is emergent before vaccination phase.
- If the partial start date is equal or after (\geq) the first study vaccination (i.e., year or year & month is/are after or the same as the first study injection year or year & month) then the adverse event is emergent during vaccination phase.

The **maximum event severity** is the greatest severity associated with a preferred term for a reported adverse event according to the following order: Mild < Moderate < Severe. Unknown/ Missing severity is considered as severe (except for the definition of emergence).

Multiple AEs with the same PT for the same subject are counted only once.

Vaccination-related Adverse Events are those for which the cause has been evaluated by the investigator, and recorded either as possibly related, probably related or unknown/missing.

Safety Laboratory Data

All laboratory measurements summarized in the CSR are those defined in the study protocol.

Reference ranges used to categorize the results as “low” (values below the lower limit of the reference range), “normal” (values within the reference range) or “high” (values above the upper value of the reference range) will be those provided by the site lab which performed the tests and provided the laboratory reports.

Prestudy, Concomitant and Post-Vaccination Medications

A **previous medication** is a medication used only before the first study vaccination (i.e. medication end date < first study vaccination date).

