13.5 Clinical Safety Laboratory Investigations

Clinical safety laboratory values, and change-from-baseline values (day x to day 1), will be summarized (mean, standard deviation, median, minimum and maximum) at each time-point of assessment, by vaccine group, for the subset of subjects in the Overall Safety Set with available laboratory data.

The frequencies of subjects with clinical laboratory values below, within, or above normal ranges will be tabulated for each clinical laboratory variable by vaccine-group and time-point of assessment (3 x 3 shift tables).

A summary of clinically significant laboratory abnormalities by time point will be provided.

Laboratory values that are outside the normal range will also be flagged in the data listings, along with corresponding normal ranges and assessment of clinical significance.

For subjects presenting at least one clinically significant value, an additional listing will be provided of all laboratory results by vaccine group, by subject, and by relevant parameter. Clinical significance assessed by the investigator will be presented.

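### The SAP text describes no table for primary endpoint (c), unsolicited AEs within 28 days after each vaccination, and it takes laboratory change from a Day 1 value that is never drawn

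*SAP*

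**What the plan says.** **Unsolicited AEs.** Protocol 8.1.1.1 defines primary endpoint (c) as "Number and percentage of subjects with reported unsolicited adverse events during 28 days following each vaccination". SAP 13.3 presents its summaries by period of onset and names one period: "Onset between day 1 and study termination". SAP 8.2.1 agrees: "The unsolicited adverse events will be analyzed in the entire study period". Table 7.7-1 has one matching set, "Safety Set, Unsolicited AEs, All study period".

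SAP 7.5 splits only the solicited sets by dose ("For the by vaccination tabulations, solicited safety sets will be defined as follows", then SOL 1 and SOL 2). SAP 8.8 does contain a dose-attribution rule, "If there are several vaccinations, the adverse event will be associated with the most recent vaccination", but no table described in the SAP text uses it. Protocol 8.4.2.1.3 has the same wide scope as the SAP: "This analysis applies to all adverse events occurring during the study".

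**Laboratory data.** SAP 13.5 states: "Clinical safety laboratory values, and change-from-baseline values (day x to day 1), will be summarized". The schedule (Protocol Table 2, and the Times and Events table in SAP 3) marks safety blood at screening and at Visits 2, 3, 4 and 5, and leaves Visit 1 blank. Protocol 3.1 treats the safety laboratory tests taken before Visit 1 as the baseline.

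**The concern.** Endpoint (c) is a primary endpoint, and carrying out the SAP text as written does not yield it. A single whole-study percentage does not show whether events followed the first or the second injection. That matters more than usual here because the comparator changes between injections, Menveo first and Boostrix second. A pooled table cannot compare the study vaccine with the control vaccine given at the same visit. The denominator is also affected: a subject withdrawn from the second vaccination (Protocol 3.7 and 3.9) stays in the single unsolicited set although never exposed to dose 2.

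The laboratory rule has a different fault. It refers to a value that does not exist, so someone must choose another baseline at the programming stage. Neutrophil change is among the affected summaries, and neutropenia is an AESI.

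Two smaller discrepancies concern solicited AEs. SAP 13.2 lists a 2-hour time point where the schedule has 30 and 60 minutes, and it omits the day 1-3 and day 4-7 intervals required by Protocol 8.4.2.1.2.

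**Working it through.** **1. Is there a Day 1 safety draw? Check against the stated blood volume.** Protocol 3.5 gives a total of 80 mL per subject.

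- Screening: 1 × 10 = 10 mL
- Serology (before each vaccination and 28 days after the second): 3 × 10 = 30 mL
- Safety (7 and 28 days after each vaccination): 4 × 10 = 40 mL
- Sum: 10 + 30 + 40 = 80 mL, which reproduces the stated figure

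A Day 1 safety draw would make it 90 mL. The volume and the schedule agree: 0 of 72 subjects have a scheduled Day 1 safety value.

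**2. What does *each vaccination* mean?** Endpoint (a) uses the same phrase with a 7-day window. The SAP carries (a) out by dose, with SOL 1 and SOL 2 in 7.5 and tabulation after each and after any vaccination in 13.2 (Level 4). Endpoint (c) has no counterpart to either.

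**3. How far does the single onset period differ from the two windows?** Visit 3 is 28 to 35 days after Visit 1, and Visit 5 is 28 to 35 days after Visit 3. Each window is taken as the injection day plus the following 28 days, as in the Protocol synopsis.

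| Visits | Study days | Covered by the windows | Outside |
|---|---|---|---|
| Both on time | 1-57 | 1-29 and 29-57 | 0 of 57 |
| Both at +7 | 1-71 | 1-29 and 36-64 (58 days) | 30-35 (6) + 65-71 (7) = 13 of 71 = 18.3% |

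SAP 13.3 can be read as counting the injection day inside the 28. The figures then become 1 of 57 and 15 of 71 (21%).

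What the extra days add depends on the recording rule. Under SAP 13.3 they add only SAEs, AESIs and AEs leading to withdrawal. Under the Protocol synopsis and 3.1, which collect any unsolicited AE through the whole study, they add all unsolicited AEs.

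**4. What does pooling hide?** Let a1 and a2 be the numbers of subjects with an AE after doses 1 and 2, and k the number with an AE after either. Then max(a1, a2) ≤ k ≤ a1 + a2. For an illustrative k = 9 of 24 controls, a1 can be anything from 0 to 9, that is 0% to 9/24 = 37.5%.

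In the other direction, assume a 10% rate after each dose (the rate used in the Protocol's sample-size statement). The whole-study percentage would be 1 − 0.9² = 19% if the two periods were independent, and between 10% and 20% under any dependence.

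**The case against.** The SAP follows the protocol's own analysis section: Protocol 8.4.2.1.3 also covers the whole study with no split by dose. Endpoint (c) could be read as the union of the two windows, since the objective concerns a two-injection regimen and the control arm is handled as one sequence. With on-time visits the single period then loses nothing. The full table list is in a separate table of contents that was not available, and the attribution rule in SAP 8.8 would have little purpose unless some output used it. The 18% is a share of calendar days at the extreme of the visit windows, not of events. The laboratory point is a wrong label, because only one pre-vaccination draw is scheduled.

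Much of this is fair. The mismatch does begin inside the protocol, so Protocol 8.4.2.1.3 needs reconciling too. The finding concerns the SAP text and cannot exclude a by-dose table elsewhere. The day count is an upper limit, and the laboratory correction is one line.

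The union reading does not stand: the SAP treats the identically worded endpoint (a) dose by dose. Nor does an unseen table list replace stating the analysis of a primary endpoint in the plan. SAP 8.8 makes the split derivable, but it has no 28-day limit and no described summary calls on it.

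**Conclusion.** Both parts hold. As written, the SAP text gives no by-vaccination, 28-day table for primary endpoint (c), and its laboratory change scores cannot be computed. If the shift tables use the same baseline, their baseline side cannot be filled either.

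The main loss for endpoint (c) is the split by dose. The onset-window mismatch is secondary: between 0 of 57 and 13 of 71 days (18%), depending on visit timing, or up to 15 of 71 (21%) on the inclusive count. Endpoint (b), the out-of-range counts by time point, needs no baseline and is unaffected.

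Onset dates are collected, so the split can be recovered. This should be fixed, but it does not threaten the trial. The conclusion rests on the SAP text alone and on reading endpoint (c) per dose, as the SAP reads endpoint (a). The two solicited-AE discrepancies are minor.

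**What to change.** - **SAP 13.3:** add n (%) tables by group for unsolicited AEs with onset within 28 days after vaccination 1 and, separately, after vaccination 2. Use the SAP 8.8 attribution rule, with recipients of that vaccination as denominator, and state whether the injection day counts within the 28. Keep the whole-study table.
- **SAP 8.8:** extend the before/after-injection timing variable to the second injection day, so that an event starting on Day 29 before the injection is assigned to dose 1.
- **SAP 7.5 and Table 7.7-1:** add unsolicited sets for periods 1 and 2, as already done for solicited AEs.
- **Protocol 8.4.2.1.3:** reconcile its whole-study scope with endpoint (c), and align the differing statements of how long ordinary unsolicited AEs are recorded.
- **SAP 13.5:** define laboratory baseline as the last value before vaccination 1 (screening), for both change scores and shift tables.
- **SAP 13.2 (minor):** reconcile the early time points with the scheduled 30- and 60-minute assessments, and restore the day 1-3 and day 4-7 intervals.

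The cost is wording and a few more tables from data already collected, with no new visits or samples. The changes should be made before unblinding.
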